# 4. SELECTION OF STUDY POPULATION

## 4.1 INCLUSION CRITERIA

# 4.1.1 Healthy Volunteers Without *Helicobacter pylori* infection

Healthy volunteers who meet all the following inclusion criteria are eligible to enroll:

- 1. At least 18 years old at the time of providing informed consent in a manner approved by the University of New Mexico, Institutional Review Board and willing to comply with the requirements of the study
- 2. In generally good health as determined by the investigator, with no respiratory illness within 2 weeks before the screening visit and no pulmonary history
- 3. No history of allergy or asthma
- 4. Has not smoked tobacco within 6 months before the screening visit and agrees not to smoke until after the follow up visit
- 5. FEV1 at least 80% at the time of providing informed consent

# 4.1.2 Healthy Volunteers Diagnosed With *Helicobacter pylori* infection

Healthy volunteers diagnosed with *H. pylori* infection who meet all the inclusion criteria for healthy volunteers in Section 4.1.1 and additionally who have diagnosed with *H. pylori* infection are eligible to enroll.

# 4.1.3 Inclusion Criteria for Subjects With Cystic Fibrosis

Subjects who meet all the following inclusion criteria are eligible to enroll.

- 1. At least 18 years old at the time of providing informed consent in a manner approved by the University of New Mexico, Institutional Review Board and willing to comply with the requirements of the study
- 2. Diagnosed with CF at least 24 months before the screening visit
- 3. Documented presence of *Pseudomonas aeruginosa* in at least three sputum cultures within 2 years before the screening visit, one of which within 6 months before the screening visit
- 4. Is able to produce sputum at the time of the screening visit
- 5. FEV1>60% or 1.5 L at the time of providing informed consent

6. Has not smoked tobacco within 6 months before the screening visit and agrees not to smoke until after the follow up visit

## 4.2 EXCLUSION CRITERIA

Subjects who meet any of the following exclusion criteria are not eligible to enroll.

- 1. Positive H. pylori serology, except for subjects in the H. pylori cohort
- 2. Subjects intolerant of albuterol
- 3. Subjects diagnosed with asthma
- 4. Subjects with evidence of upper respiratory tract infection within 14 days before the screening visit
- 5. Use of inhaled antibiotics within 12 hours before the administration of the breath test on Day 1 or required use of inhaled antibiotics during the study
- 6. Has smoked tobacco within 6 months before the screening visit
- 7. Females who are pregnant or nursing or of child-bearing potential who are not using a medically acceptable form of contraception (acceptable forms of contraception are hormonal birth control, intrauterine device, or barrier method plus a spermicidal agent) or abstinence
- 8. Any condition or history that, in the judgment of the investigator, would compromise the ability of the subject to comply with the study protocol or to complete the study
- 9. Subjects who have used an investigational agent within 28 days before Day 1

## 4.3 REMOVAL OF SUBJECTS

Subjects may be removed from the study by the investigator at any time for any of the following reasons:

- 1. Adverse event
- 2. Non-compliance with study protocol
- 3. Any condition that, in the judgment of the investigator, would compromise the ability of the subject to comply with the study protocol or to complete the study

In addition, subjects may remove themselves from the study at any time for any reason without consequence to further treatment by the investigator.

All subjects who are removed prematurely from the study should be assessed according to the procedures and assessments scheduled for the end-of-study visit in Section 6.3.

## 4.4 REPLACEMENT OF SUBJECTS

Subjects who are removed from the study prematurely will be replaced in order to maintain the required number of subjects in each cohort.

# 5. PROCEDURES FOR ADMINISTRATION OF TREATMENTS

All investigational medications will be prepared and dispensed by the investigational pharmacist or delegate at the University of New Mexico Hospital in accordance with procedures in this protocol.

## 5.1 TREATMENTS TO BE ADMINISTERED

## 5.1.1 Identification of Investigational Product

The active pharmaceutical ingredient is lyophilized C-urea; the carbon content is enriched in C (at least 99%), a naturally-occurring, non-radioactive isotope of carbon (Table 2).

 Table 2
 Identification of Investigational Product

	Study Product
Active Substance (INN)	 C-urea
Trade Name (if applicable)	Not applicable
Formulation (including dosage form and strength)	Lyophilisate to be reconstituted with 3 mL of sterile water for injection to form isotonic solutions of pH 7.2 containing 20 mg or 50 mg of active ingredient
Route/Mode of Administration	Inhalation
Manufacturer	Coldstream Laboratories, Lexington, Kentucky USA

# 5.1.2 C-urea Breath Test Kit

The C-urea breath test kit in this study contains C-urea lyophilized in a 10 mL glass vial with an aluminum crimp closure, 3 mL of sterile water for injection (WFI), a nebulizer cup (LC Sprint Star reusable nebulizer cup, PARI, Midlothian, Virginia, part number 023F35), 12 300-mL mylar breath collection bags (Meretek, Rockville, Maryland), and plastic tubing to connect the nebulizer cup to the compressor (Vios™ Adult Aerosol Delivery System, PARI, Midlothian, Virginia, part number 310F35-LCS). Additionally, each kit will contain 24 self-adhesive bar-code stickers used to identify collection bags and to maintain integrity of data collection. The lyophilisate will be reconstituted by transferring WFI using a 3 mL syringe (Becton Dickinson, Franklin Lakes, New Jersey, part number 309595). All components will be supplied sterile; all are intended for single use.

# 5.1.3 Administration of Study Drug

The lyophilisate will be reconstituted in WFI (3 mL) supplied with the breath test kit and administered by inhalation.). If all the reconstituted study drug does not go into solution, or if

the reconstituted solution is cloudy or contains particulate material, the vial will be discarded. The nebulizer cup is connected to the compressor with the supplied tubing, and the entire clear, reconstituted solution of C-urea is transferred into the nebulizer cup. After turning on the compressor, the subject will inhale the study drug by breathing through the mouthpiece of the nebulizer cup until all the solution has been aerosolized and inhaled (Appendix A).

## 5.1.4 Pre-treatment

Subjects with CF will receive two puffs of albuterol (90 µg albuterol base per puff) from a standard holding chamber (Aerochamber, Lupin Pharmaceuticals, Baltimore, Maryland) 10 minutes before the administration of study drug (Table 3).

**Table 3 Identification of Pre-treatment** 

-	Study Product
Active Substance (INN)	Albuterol
Trade Name (if applicable)	Ventolin HFA
Formulation (including dosage form and strength)	Aerosol (108 μg albuterol sulfate, 90 μg albuterol base from mouthpiece per actuation)
Route/Mode of Administration	Inhalation
Source	GlaxoSmithKline

## **5.1.5** Rescue Medication

In the event of wheezing or bronchospasm following administration of study drug, albuterol may be administered as rescue medication.

# 5.1.6 Methods of Assigning Subjects to Treatment Group

Subjects without *H. pylori* infection will be assigned to a single, open-label treatment, beginning with the lower dose of study drug, in the order in which they enter the study according to the dose escalation rules in Table 1 (Section 3.1.3). Healthy volunteers diagnosed with *H. pylori* infection will received the MTD.

# **5.1.7** Selection of Doses in the Study

Enrolled subjects will receive single doses of C-urea 20 mg or 50 mg.

# 5.1.8 Selection and Timing of Doses for Each Subject

Subjects will receive single doses of C-urea in increasing amounts, 20 mg in the first cohort and 50 mg in the second cohort as detailed in Table 1. Study drug may be administered in the fasted or as-fed state, but subjects should not ingest food until after the last breath sample is

collected; subjects may receive water *ad libitum*. Subjects may be administered study drug at any time of day with the provision they are required to be available 24 hours after the study drug is administered for a follow-up evaluation.

## 5.1.9 Blinding

This is an open-label study.

# 5.1.10 Packaging and Labeling

Lyophilized C-urea 20 mg and 50 mg will be supplied in 10 mL stoppered vials sealed with aluminum closures and labeled for investigational use only. Study drug will be reconstituted in WFI (3 mL) supplied with the breath test kit and administered by inhalation (see Table 2 for the identification of the investigational product).

# **5.1.11 Storage**

C-urea should be stored at ambient conditions (from 15° to 30° C [59° to 86° F]) in an area restricted to investigational staff or the pharmacy at the study center.

# 5.1.12 Accountability and Destruction of Study Drug

All investigational medications will be signed for by the investigational pharmacist at the University of New Mexico (or designee) when they are received. The study drug must be handled and stored as described and dispensed only to those subjects formally entered into the study.

At the completion of the study, and after reconciliation of all delivery and usage records, any unused study drug will be destroyed.

### 5.2 CONCOMITANT THERAPY

With the exception of inhaled antibiotics, subjects are allowed concomitant medications for pre-existing conditions as deemed necessary by the investigator from the time of study drug inhalation until the last breath sample is collected. Drugs taken from the beginning of inhalation of study drug until the follow-up visit will be recorded on the CRF. The generic name of the drug, the dose, and the time and reason for administration will be recorded on the CRF.

Inhaled antibiotics are disallowed from the beginning of the inhalation of study medication until the collection of the final breath sample at 2 hours.

# 5.3 TREATMENT COMPLIANCE

As all subjects will receive study drug in the clinic under supervision of study personnel, each subject will be considered treatment compliant who inhales the full volume of reconstituted study drug.

# 6. VISIT SCHEDULE

The schedule of assessments and procedures are summarized in Table 4.

Table 4 Schedule of Procedures and Assessments for Dose-ranging Study

Assessment/Procedure	Screening (Day -7 to Day -1)	Day 1	Follow-up a
Informed consent	X		
Inclusion/exclusion criteria	X	X	
Medical history	X		
Concomitant medications, including all medications taken within the last 48 hours	X	X	X
Twelve-lead electrocardiogram	X		
Helicobacter pylori serology	X		
Urine pregnancy test (child-bearing females)		X	
Five-minute vital signs measurements c		X	
Respiratory examination (respiration rate, auscultation, pulse oximetry, and related symptoms, such as cough)		X	
Perform spirometry	Xb	X	
Administer albuterol (subjects with cystic fibrosis only)		X	
Perform spirometry d		X	
Obtain sputum specimen		Xe	
Perform breath test f		X	
Assess adverse events		X	Xg

<sup>a Subjects will be contacted by telephone 24 hours after administration of study drug for a follow-up assessment.

b Spirometry does not need to be performed at the screening visit if performed within the past 14 days.

<sup>c Heart rate, systolic and diastolic blood pressure, and body temperature will be recorded before study drug administration to assist in the determination that enrolled subjects are in generally good health.

d Spirometry will be performed before and at 10 and 30 min after the end of study drug administration. In addition, only for subjects with cystic fibrosis, spirometry will be performed before and  $10 \pm 2$  minutes after pre-treatment with albuterol.

<sup>e Sputum specimens will be collected immediately after performing baseline spirometry only from subjects with cystic fibrosis. Sputum specimens will be cultured to determine the identity and number of pathogens, and will also be qualitatively analyzed nonselectively for the presence of urease-producing bacteria using a colorimetric assay.

f Study drug will be administered immediately following spirometry, or for subjects with cystic fibrosis, the collection of sputum. Five baseline exhaled breath specimens will be obtained immediately before administration of  $^{13}$ C-urea. Exhaled breath specimens will be collected at  $5 \pm 1$ ,  $10 \pm 2$ ,  $15 \pm 2$  (in triplicate at this timepoint only) after administration of  $^{13}$ C-urea and sent within 24 h after collection to the central laboratory for analysis.

g Subjects who report adverse events at the follow-up assessment will be asked to return to the clinic for evaluation.

# 6.1 SCREENING (DAY -7 TO DAY -1)

The following procedures and assessments will be performed at the screening visit (Day -7 to Day -1).

- 1. Acquire written informed consent.
- 2. Review inclusion and exclusion criteria.
- 3. Document medical history, including all medications taken within 48 hours before the administration of study drug.
- 4. Obtain a 12-lead electrocardiogram (ECG).
- 5. Collect a blood specimen (5 mL) to assess *H. pylori* infection.
- 6. Perform spirometry, if not performed within the previous 14 days (Section 7.2.1).

# 6.2 ACTIVE TREATMENT (DAY 1)

- 1. Review inclusion and exclusion criteria.
- 2. Document all medications taken within the last 48 hours.
- 3. Perform a urine pregnancy test on women of child-bearing potential.
- 4. Record 5-minute sitting vital signs measurements (heart rate, systolic and diastolic blood pressure, and body temperature).
- 5. Perform respiratory examination (respiration rate, auscultation [presence of wheezing and crackles], pulse oximetry, and related symptoms, such as cough) (Section 7.2.1).
- 6. Perform spirometry (Section 7.2.1).
- 7. Administer albuterol, only to subjects with CF (Section 5.1.4).
- 8. Perform baseline spirometry  $10 \pm 2$  minutes after administering albuterol to subjects with CF only (Section 7.2.1).
- 9. For subjects with CF only, collect sputum specimen.
- 10. Collect five breath specimens. Record the clock time at which the sample was collected on two self-adhesive stickers. Place one sticker on the collection bag and the other on the CRF (Section 7.1.2.1).
- 11. Administer study drug by inhalation (Section 5.1.3). Record the clock time at the beginning and end of study drug administration.
- 12. Measuring time from the end of the inhalation of study drug, collect breath specimens at  $5 \pm 1$ ,  $10 \pm 2$ ,  $15 \pm 2$  minutes (three specimens at this time point only) after the inhalation of study drug is completed. Record the clock time of each breath collection on two self-adhesive stickers. Place one sticker on the collection bag and the other on the CRF (Section 7.1.2.1).
- 13. Perform spirometry after collecting the breath specimen at 10 and 30 minutes after the end of study drug administration (Section 7.2.1).
- 14. Assess adverse events (Section 8).

# 6.3 FOLLOW-UP

Twenty-four hours after administration of study drug, subjects will be contacted by telephone and asked a non-leading question to assess adverse events such as "How do you feel after participating in the study?" Additionally, subjects will be asked if they have taken any

medications since receiving study drug. All medications taken from the time of study drug administration until the follow-up assessment will be recorded on the CRF. Subjects who have adverse events at the follow-up visit will be asked to return to the clinic for evaluation.

#### 6.4 DISCONTINUATION

Subjects who discontinue from the study prematurely will receive a follow-up assessment (Section 6.3).

# 7. STUDY VARIABLES AND METHODS OF ASSESSMENT

## 7.1 EFFICACY VARIABLE

## 7.1.1 Overview of Variable

The C-urea breath test will be administered to all subjects after performing baseline spirometry.

## 7.1.2 Methods of Assessment

# 7.1.2.1 Collection of Breath Specimen

Samples of exhaled breath will be collected immediately before and at  $5 \pm 1$ ,  $10 \pm 2$ ,  $15 \pm 2$  minutes after the inhalation of study drug is completed. Five breath specimens will be obtained before the inhalation of study drug; one specimen will be obtained at each subsequent assessment except for the 15-minute assessment at which time three exhaled breath specimens will be obtained. Step-wise instructions for performing the breath test are provided in Appendix A.

- 1. Record the clock time, intended sample time (e.g., baseline, 5-minute), and subject demographic information on two self-adhesive stickers in the C-urea breath test kit. Place one of the stickers on the breath collection bag and the other sticker on the CRF.
- 2. Remove the pull-off cap from the mouthpiece of the breath collection bag.
- 3. Instruct the subject to breath normally, then take a deep breath and pause momentarily before exhaling into the mouthpiece of the bag.
- 4. Place the cap on the mouthpiece of the bag until it clicks into place.
- 5. Store the breath specimen at 15° to 30° C (59° to 86° F) until analyzed.

# 7.1.2.2 Analysis of Breath Specimen

After collection, all breath test specimens will be picked up within 24 hours by the central laboratory to be analyzed within 7 days of collection. The isotopic ratio of  $^{13}$ C to  $^{12}$ C is calculated from breath samples collected before and after administration of  $^{13}$ C-urea using a POCone® Infrared Spectrophotometer (Otsuka America Pharmaceutical, Rockville, Maryland). The relative increase in isotopic ratio,  $\delta$ , is determined automatically by the spectrophotometer (I).

$$\delta = \left(\frac{R_x - R_{std}}{R_{std}}\right) \times 1000, \tag{I}$$

where  $R_x$  is the ratio of the abundance of  $^{13}C$  to  $^{12}C$  in the post-administration sample and  $R_{std}$  is the corresponding ratio at baseline.

# 7.1.3 Microbial Analysis of Sputum

# 7.1.3.1 Overview of Variables

Sputum specimens will be obtained from subjects with CF after the performance of baseline spirometry and before administration of study drug. Specimens will be obtained using standard practices at the study site, and in all cases will be expectorated into a sterile sputum cup, labeled with the time of day, date, and unique study identifier for that patient.

# 7.1.3.2 Methods of Assessment

The presence of urease-containing bacteria will be determined locally using a colorimetric method in which a sample is plated in a medium that changes to a blue color as its pH is increased by the production of ammonia, a by-product of the urease-catalyzed degradation of urea (Cox et al 1977, Damato et al 1982, Isenberg 2004).

Additionally, bacterial flora in collected sputum will be assessed using standard quantitative microbiologic methods employed at the study site in which colony forming units (CFU) are identified and counted, and in all cases organisms in numbers greater than 10^4 and appearing in more than one CFU will be identified and counted.

## 7.2 SAFETY VARIABLES

The safety of C-urea will be assessed from adverse events (Section 8), spirometry test results (FEV1 and FVC), and respiratory examinations (respiratory rate, auscultation [presence of wheezing and crackles], pulse oximetry, and related symptoms, such as cough).

# 7.2.1 Spirometry

# 7.2.1.1 Overview of Variables

Spirometry will be performed at the initial respiratory examination (baseline, Day 1) and after collecting breath specimens at 10 and 30 minutes. If the last FEV1 measurement is less than 10% of baseline, 4 puffs of albuterol will be administered and spirometry will be repeated in 15 minutes. Patients will be discharged from the clinic when FEV1 is within 10% of baseline measurements and patients are symptom free. For subjects with CF, spirometry will be performed before and 10 minutes after administration of albuterol on Day 1.

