**Table 1 Dose Escalation Rules** 

Condition within 24 hours after administration of study drug	Number of DLTs/ Subjects in Cohort	Action
If no subject experiences DLT	0/3	Enroll three subjects at the 50 mg dose level
If one subject experiences DLT	1/3	Enroll three additional subjects at the 20 mg dose
If no additional subject experiences DLT	1/6	Enroll three subjects at the 50 mg dose level
If more than one subject experiences DLT	>1/6	Stop enrollment

Subjects will be receive C-urea 20 mg and 50 mg unless enrollment stops because of DLT. DLT Dose-limiting toxicity.

Sputum will be collected from each subject with CF before administering study drug in order to identify bacterial flora using two standard microbiologic methods. The first is a quantitative method in which colonies are stained and counted, the second is a colorimetric method in which a sample is plated in a medium that changes to a blue color as its pH is increased by the production of ammonia, a by-product of the urease-catalyzed degradation of urea.

The pharmacokinetics of the production of C-carbon dioxide will be characterized by determining the isotopic ratio of C to C in exhaled carbon dioxide of subjects in each part before study drug administration and at 5, 10, and 15 minutes.

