# 3.1.3.1 Dose-limiting Toxicity

The following significant respiratory events will be considered DLTs (Rosenfeld et al 2011):

- an absolute decrease from baseline FEV1 of 20% of baseline or greater
- an absolute decrease from baseline oxygen saturation of at least 10%
- an increase from baseline respiratory rate of 10 breaths per minute for more than 2 minutes during quiet breathing
- new wheezes or rales on examination.

In addition to these events that are mandated DLT, the data safety monitor may determine any serious adverse event attributed to study drug to be dose limiting.

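### In CF subjects, baseline FEV1 names two different Day 1 readings and no section says which governs the 20% dose-limiting toxicity; the rescue-albuterol trigger is also misworded

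*Protocol*

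**What the plan says.** Section 6.2 orders Day 1 as follows: respiratory examination (step 5), spirometry (step 6), albuterol for CF subjects only (step 7), a second spirometry 10 ± 2 minutes later for CF subjects only (step 8), sputum from CF subjects (step 9), pre-dose breath specimens (step 10), study drug (step 11). CF subjects therefore have two spirometries before study drug, and healthy volunteers have one. Table 4 footnote d confirms the extra CF readings: "In addition, only for subjects with cystic fibrosis, spirometry will be performed before and" again after the albuterol pre-treatment.

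The word baseline is attached to these readings in several places:

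- 7.2.1.1, for all subjects: "Spirometry will be performed at the initial respiratory examination (baseline, Day 1".
- 6.2 step 8, for the post-albuterol CF reading: "Perform baseline spirometry". Step 6 does not carry the word.
- Table 4 footnote e: "Sputum specimens will be collected immediately after performing baseline spirometry only from subjects with cystic fibrosis".
- 7.1.3.1: "Sputum specimens will be obtained from subjects with CF after the performance of baseline spirometry and before administration of study drug".
- 7.1.1: the breath test is "administered to all subjects after performing baseline spirometry".

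These rules depend on baseline FEV1 without naming the reading:

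- 3.1.3.1 makes an FEV1 decrease "of 20% of baseline or greater" a mandated DLT.
- 7.2.2.1 requires post-dose auscultation only at an assessment where FEV1 has fallen at least 20% from baseline.
- 7.2.1.1 gives four puffs of albuterol when the last FEV1 is under 10% of baseline, and allows discharge once FEV1 is no more than 10% away from baseline and the subject has no symptoms.
- 3.1.3 and 3.2.2 state a stricter discharge rule: saturation and FEV1 back at baseline, and cough resolved.

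Under Table 1, one DLT among three subjects leads to "Enroll three additional subjects at the 20 mg dose"; none among three leads to the 50 mg level. Section 1.5 applies the same escalation design to CF subjects.

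**The concern.** A DLT rule needs one reference value. In CF subjects the protocol gives that name to two readings, with a bronchodilator between them. If site staff take the 7.2.1.1 label at face value, any FEV1 gain from albuterol is added to the room a subject has before a fall after study drug counts. A fall of just over 20% from the level at which the subject actually received study drug would then not be a DLT.

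Two safeguards share the same reference. The first is the FEV1 criterion itself. The second is the scheduled auscultation in 7.2.2.1, which is how the separate DLT of new wheezes or rales would be found after dosing. An FEV1 fall that goes unrecognised also leaves that examination untriggered. The saturation and respiratory-rate criteria do not refer to FEV1.

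Cohorts have three subjects, so one reclassified subject changes the Table 1 action. These decisions are taken while the trial runs, with data going daily to the data safety monitor (8.5), so a later statistical analysis plan cannot settle them.

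The rescue trigger is a separate wording fault in the same section and applies to every subject.

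**Working it through.** **Which reading each section points to.** The initial respiratory examination in 7.2.1.1 corresponds to steps 5 and 6 of 6.2, before albuterol at step 7. Section 7.2.1.1 does not itself say pre-albuterol; that follows from the step order. Step 8 labels the post-albuterol reading. Sputum is step 9, so footnote e (immediately after baseline spirometry) fits step 8, and 7.1.3.1 agrees. Section 7.1.1 is compatible with step 8 but does not decide the matter. The balance favours the post-albuterol reading, but none of these sections refers to the DLT, auscultation, rescue or discharge rules.

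**Size if the pre-albuterol reading were used.** The protocol gives no albuterol response. Let b be the proportional FEV1 gain, assumed at 5, 10 or 15%, so that the immediate pre-dose value is (1 + b) times the pre-albuterol value.

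- Fall from the pre-dose value needed for a DLT: 1 − 0.8/(1 + b)
- Recorded change when the true fall is 20%: 0.8(1 + b) − 1
- Fall tolerated by the 10% discharge rule (7.2.1.1): 1 − 0.9/(1 + b)
- Fall tolerated by the return-to-baseline discharge rule (3.1.3, 3.2.2): 1 − 1/(1 + b) = b/(1 + b)

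| b | Fall needed for DLT | Recorded change for a true 20% fall | Tolerated, 10% rule | Tolerated, return to baseline |
|---|---|---|---|---|
| 0% | 20.0% | −20.0% | 10.0% | 0.0% |
| 5% | 23.8% | −16.0% | 14.3% | 4.8% |
| 10% | 27.3% | −12.0% | 18.2% | 9.1% |
| 15% | 30.4% | −8.0% | 21.7% | 13.0% |

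With the post-albuterol reference, the b = 0% row applies whatever the albuterol response.

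**Example at b = 10% (assumed volumes).** FEV1 is 2.00 L before albuterol, 2.20 L after albuterol and 1.70 L after study drug.

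- Against 2.20 L: 1.70/2.20 − 1 = −22.7%. This is a DLT and triggers auscultation; if it is the only one, the cohort stands at 1/3.
- Against 2.00 L: 1.70/2.00 − 1 = −15.0%. This is not a DLT, no auscultation is scheduled, and the cohort stands at 0/3.

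**Rescue trigger on a 2.00 L baseline.** As written: 0.10 × 2.00 = 0.20 L, a fall of more than 90%. As the discharge sentence that follows it implies: 0.90 × 2.00 = 1.80 L, a fall of more than 10%.

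**The case against.** The strongest reply is that the protocol already answers the question. Section 6.2 is the sequence that staff follow on the day, and only step 8 carries the baseline label there. The sputum instructions agree with it. The sentence in 7.2.1.1 is general and covers all subjects, and the specific CF step should prevail. On that reading nothing is masked. This largely stands, and it limits the point to an unresolved definition. It does not remove the point, because step 8 refers staff to 7.2.1, the section that labels the other reading, and the DLT rule names neither.

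A second reply is that the consequence needs several things at once: use of the pre-albuterol value, a material albuterol gain, and a fall between 20% and the raised threshold. The 50 mg dose will by then have been reviewed in healthy volunteers. The data safety monitor sees each subject's data and can stop escalation at discretion (3.2). All of this is true and limits the likely harm, but it does not define the baseline.

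A reader might infer more than the documents support in three ways:

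- That the protocol sets a pre-albuterol reference and so will under-count DLTs in CF. It does not; the better-supported reading gives no bias.
- That subjects with a true 20% fall would be sent home. Under the 10% rule this needs 0.8(1 + b) ≥ 0.9, so b ≥ 12.5%, and absence of symptoms as well. Under the return-to-baseline rule it needs 0.8(1 + b) ≥ 1, so b ≥ 25%.
- That the rescue wording would leave subjects untreated. Section 5.1.5 permits albuterol for wheezing or bronchospasm, the discharge rules hold subjects until FEV1 recovers, and the intended limit is plain from the following sentence.

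**Conclusion.** The point holds as a defect of definition in rules that act during the trial. In CF subjects two Day 1 readings are called baseline, and nothing ties either to the 20% FEV1 DLT, the auscultation trigger, or the rescue and discharge rules. The post-albuterol reading is the better supported. If the other were used, an assumed albuterol gain of 5 to 15% would move the DLT threshold from 20% to between 23.8% and 30.4% of the immediate pre-dose value, and one missed DLT would change the Table 1 action. At zero gain, or with the post-albuterol reading, there is no effect. The sizes rest wholly on the assumed gain.

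The reach is modest: 6 CF subjects of about 15 planned. Healthy volunteers have a single Day 1 pre-dose reading and are not affected by the baseline conflict. The rescue trigger is wrong as written for everyone, but its meaning can be recovered and its likely harm is small. Both should be corrected.

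**What to change.** In 3.1.3.1, 7.2.1.1 and 7.2.2.1, define baseline FEV1 as the last spirometry before study drug: the post-albuterol reading in CF subjects (step 8 of 6.2), and the single Day 1 pre-dose reading in healthy volunteers. State that this value is used for the DLT, auscultation, rescue and discharge rules, including the discharge wording in 3.1.3 and 3.2.2. Remove the baseline label from the initial-examination spirometry in 7.2.1.1 where it would apply to CF subjects.

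In 7.2.1.1, reword the rescue trigger so that albuterol is given when the last FEV1 is more than 10% below baseline.

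The cost is wording only. Both spirometries are already scheduled, and no assessment, visit or subject is added.

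### Protocol 7.2.1.1 sets the albuterol and repeat-spirometry trigger at an FEV1 below 10% of baseline, where a fall of more than 10% must be meant; which test is the CF baseline also needs settling

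*Protocol*

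**What the plan says.** **Trigger.** After the scheduled post-dose spirometry at 10 and 30 minutes, Section 7.2.1.1 requires action if the last FEV1 "measurement is less than 10% of baseline, 4 puffs of albuterol will be administered and spirometry will be repeated in 15 minutes". The next sentence lets a subject go home once FEV1 "is within 10% of baseline measurements and patients are symptom free". Section 3.1.3.1 makes an FEV1 decrease "of 20% of baseline or greater" a mandated DLT. The protocol does not state the albuterol trigger anywhere else.

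**CF baseline.** Section 7.2.1.1 opens with a sentence for all subjects: "Spirometry will be performed at the initial respiratory examination (baseline, Day 1"). Its closing sentence on CF subjects calls for one test before albuterol and one 10 minutes after it, and calls neither of them baseline. In Section 6.2 the respiratory examination and first spirometry are steps 5 and 6, and albuterol is step 7. Step 8 then reads "Perform baseline spirometry" at 10 ± 2 "minutes after administering albuterol to subjects with CF only". Sputum collection is step 9. Table 4 footnote e says "Sputum specimens will be collected immediately after performing baseline spirometry only from subjects with cystic fibrosis", and Section 7.1.3.1 says "Sputum specimens will be obtained from subjects with CF after the performance of baseline spirometry and before administration of study drug". Section 3.1.3.1 does not say which test is the CF baseline.

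**The concern.** The trigger is a safety instruction in a study that Section 1.5 describes as the first in humans of this breath test, and cough and bronchospasm are recognised risks (Section 1.3). A fall of 10% to 20% is short of a DLT and also short of the 20% fall at which Section 7.2.2.1 requires auscultation. In that range this sentence is the only provision that mandates treatment and fixes a time for a repeat test. As written, it does not reach those subjects.

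For CF subjects, the choice of baseline moves the trigger, the discharge value and the 20% DLT limit together. Table 1 acts on DLT counts in cohorts of three, and Section 1.5 applies the same escalation design to CF subjects. DLT and discharge decisions are made during the study (under Section 8.5 the data safety monitor sees data daily), so a definition that appeared only in a separate analysis plan would not govern them.

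**Working it through.** No sample size or error rate is involved; the check is threshold arithmetic. The percentages come from Sections 7.2.1.1 and 3.1.3.1. The protocol gives no FEV1 values in litres for a typical subject and no albuterol response, so those are assumptions.

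**1. Trigger.** Let B be baseline FEV1.

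- As written: FEV1 < 0.10 × B, a fall of more than 90%.
- Complement of the discharge rule: FEV1 < 0.90 × B, a fall of more than 10%.
- DLT limit: FEV1 ≤ 0.80 × B.

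| Assumed B (L) | As written (L) | As intended (L) | DLT limit (L) |
|---|---|---|---|
| 1.50 | < 0.15 | < 1.35 | ≤ 1.20 |
| 2.00 | < 0.20 | < 1.80 | ≤ 1.60 |
| 3.00 | < 0.30 | < 2.70 | ≤ 2.40 |
| 4.00 | < 0.40 | < 3.60 | ≤ 3.20 |

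At every baseline the written trigger lies far below the DLT limit, so the albuterol step would begin only long after the event that it should precede. Example with B = 3.00 L: a last FEV1 of 2.55 L is 2.55/3.00 = 85.0% of baseline, a 15.0% fall. The intended rule calls for 4 puffs and a 15-minute re-test; the written rule calls for neither.

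**2. CF baseline.** By the step order in 6.2, the test at the initial examination precedes albuterol. Assume 2.00 L before albuterol and a response of 5%, 10% or 15%.

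| Baseline used | B (L) | 0.90 × B (L) | DLT limit 0.80 × B (L) | Fall if post-dose FEV1 is 1.70 L |
|---|---|---|---|---|
| Pre-albuterol | 2.00 | 1.80 | 1.60 | 1 − 1.70/2.00 = 15.0%, no DLT |
| Post-albuterol, +5% | 2.10 | 1.89 | 1.68 | 1 − 1.70/2.10 = 19.0%, no DLT |
| Post-albuterol, +10% | 2.20 | 1.98 | 1.76 | 1 − 1.70/2.20 = 22.7%, DLT |
| Post-albuterol, +15% | 2.30 | 2.07 | 1.84 | 1 − 1.70/2.30 = 26.1%, DLT |

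For a post-dose value of 1.70 L the call changes once the post-albuterol baseline reaches 1.70/0.80 = 2.125 L, a response of 2.125/2.00 − 1 = 6.25%. In general the call differs only when the post-dose value lies between the two DLT limits, for example above 1.60 L and up to 1.76 L at a 10% response. With no response the limits coincide. With a 5% drop after albuterol the post-albuterol limit is 0.80 × 1.90 = 1.52 L, and the direction reverses.

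**The case against.** **On the trigger.** Trained pulmonary staff who read the discharge sentence straight after the trigger would hardly wait for a 90% fall. A reader might infer that subjects with a marked fall would be sent home untreated. The documents do not support that. A subject 15% below baseline cannot be discharged under 7.2.1.1, nor under Sections 3.1.3 and 3.2.2, which ask for FEV1 to return to baseline. Section 5.1.5 permits albuterol for wheezing or bronchospasm, and Section 1.5 has co-investigators available on site. This stands and limits the practical harm. It does not restore the mandated dose or the 15-minute timing: rescue albuterol is optional and depends on symptoms, and withheld discharge sets neither a treatment nor a time.

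**On the CF baseline.** A reader might infer that 7.2.1.1 designates the pre-albuterol test as the baseline for CF subjects in particular. It does not. The label sits in a general sentence, which is correct for healthy volunteers, who have one pre-dose test on Day 1. The CF-specific text favours the post-albuterol test: step 8 is the only spirometry step in 6.2 called baseline, and the sputum timing fits it. A specific instruction normally governs a general one. What remains is a general label without a CF exception and a DLT definition that is silent.

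**On the DLT example.** It rests on chosen values, and at a 5% response the call does not change. At 20 mg, one extra DLT means three more subjects first, not a stop, because Table 1 still moves to 50 mg at 1/6. At 50 mg there is no further escalation to delay. All of this stands.

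**Conclusion.** The trigger is wrong as written and should be fixed. It states a limit of 10% of baseline where 90% of baseline is needed, and no other section gives the correct value. That a fall of more than 10% is meant is an inference, but the adjoining discharge rule and the 20% DLT limit leave no workable alternative. The likely practical harm is limited.

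The CF baseline is a secondary inconsistency to settle. A changed DLT call is possible only if albuterol changes FEV1 and the post-dose value falls between the two limits. The example of 2.00 L before albuterol, 2.20 L after it and 1.70 L after study drug, read as a 15.0% or a 22.7% fall, illustrates that possibility with assumed figures. The protocol offers no basis for saying how often it would occur, and the example does not show that any cohort decision would be wrong.

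**What to change.** - **Section 7.2.1.1, trigger:** replace the condition with: if the last FEV1 is more than 10% below baseline. This is the exact complement of the discharge rule that follows it.
- **Sections 7.2.1.1 and 3.1.3.1, baseline:** add one sentence to each stating that for CF subjects baseline is the post-albuterol, pre-dose test of Section 6.2 step 8. This agrees with the sputum timing and measures the effect of study drug from the state in which it is given.

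**Cost.** One phrase and two sentences, with no new scheduled procedure and no change to Table 1 or the planned 15 subjects. Two consequences should be accepted openly. When albuterol raises FEV1, the post-albuterol baseline is the stricter one and can add a DLT call, and with it three subjects at that dose under the existing rule. It also raises the FEV1 needed for discharge. In the 10% example this goes from 0.90 × 2.00 = 1.80 L to 0.90 × 2.20 = 1.98 L under 7.2.1.1, or from 2.00 L to 2.20 L under the return-to-baseline wording of 3.1.3 and 3.2.2. Those two discharge wordings differ from each other on FEV1, and the sponsor may wish to align them in the same edit.
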